FLU 150 mg/m² similar to that established in the FHCRC/OHSU Phase 1 study in the traditional donor setting with the addition of a single dose of 200 cGy TBI. Dose escalation rules are established to first increase FLU to 200 mg/m² and then increase TBI to 300, 400, and 450 cGy TBI in the event of excessive graft failures.

Previous experience with RIC UCBT suggests that patients who have had limited prior therapy are at particularly greater risk for graft failure. For the purposes of determining acceptable engraftment rates following TREO/FLU/TBI, patients will be classified as low risk for graft failure (Arm 1) or high risk for graft failure (Arm 2) as follows. For each arm, a true probability of graft failure of 5% (or less) will be accepted without dose escalation.

- Arm 1: Low-risk patients include those who have received ≥ 2 cycles of multiagent chemotherapy and at least one cycle of therapy within the 3 months previous to UCBT.
- Arm 2: High-risk patients include those who have received no multiagent chemotherapy or immune suppressive chemotherapy in the 3 months prior to transplant or have received only a single induction therapy.

We believe that a TREO/FLU based conditioning regimen may improve outcomes for acute leukemia and MDS UCBT patients unable to tolerate high-dose myeloablative therapy but at high risk for relapse. In addition to possibly improving outcomes for those RIC patients at high-risk for relapse, a TREO regimen would provide a higher intensity chemotherapeutic treatment option for patients ineligible for high dose radiation and therefore ineligible for FHCRC protocol 2010. Experience with the regimen in this setting may lead to its extension to a broader group of cord patients.

3. Objectives

A. Primary Objective:

The primary objective of this study is to show that TREO/FLU/TBI as a sufficient conditioning regimen reduces the probability of graft failure as compared to an historical benchmark and that the risk of day -200 NRM is not higher than a relevant historical benchmark. Patients will be divided into two arms based on risk of graft failure as described above.

Primary endpoints are as listed below:

1. Graft failure/rejection and secondary graft failure. Patients will be considered primary graft failure/rejections provided they meet any criteria listed below:
 - i. Absence of 3 consecutive days with neutrophils $\geq 500/\mu\text{l}$ combined with host CD3 peripheral blood chimerism $\geq 50\%$ at day 42

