 - ii. Absence of 3 consecutive days with neutrophils $\geq 500/\mu\text{l}$ under any circumstances at day 55
 - iii. Death after day 28 with neutrophil count $< 100/\mu\text{l}$ without any evidence of engraftment ($< 5\%$ donor CD3)
 - iv. Primary autologous count recovery with $< 5\%$ donor CD3 peripheral blood chimerism at count recovery and without relapse

Secondary graft failure is defined as decline of neutrophil count to <500/ μ l with loss of donor chimerism after day 55

2. Day -200 non-relapse mortality

B. Secondary Endpoints:

1. Platelet engraftment by six months
2. Grade II-IV and III-IV acute GVHD at day 100 and one year
3. Chronic GVHD
4. Clinically significant infections
5. Overall survival
6. Relapse or disease progression
7. **(FHCRC only)** Immune reconstitution
8. **(FHCRC only)** Emergence of a dominant unit

4. **Patient Selection**

A. Inclusions

1. Disease Criteria

- a. Acute Myeloid Leukemia/Acute Lymphoblastic Leukemia, including Biphenotypic Acute Leukemia or Mixed-Lineage Leukemia: Must have < 5% morphologic marrow blasts in an evaluable marrow sample (>25% of normal cellularity for age collected less than one month prior to start of conditioning. Patients in which adequate marrow/biopsy specimens cannot be obtained to determine remission status by morphologic assessment, but have fulfilled criteria of remission by flow cytometry, recovery of peripheral blood counts with no circulating blasts, and/or normal cytogenetics (if applicable) may still be eligible. Reasonable attempts must be made to obtain an adequate specimen for morphologic assessment, including possible repeat procedures. These patients must be discussed with the Principal Investigator, [name] ([name] or pager, [name]) prior to enrollment. Patients persistently aplastic for greater than one month since completing last chemotherapy are also eligible with PI approval.
- b. Myelodysplastic syndrome (MDS): Any 2001 WHO classification subtype (Appendix I). RAEB-2 patients may proceed directly to transplant, but may also be considered for induction chemotherapy before transplant. Patients with $\geq 20\%$ morphologic marrow blasts require induction therapy to reduce morphologic marrow blasts below 5% before transplant.
- c. Chronic myelogenous leukemia: All types, except refractory blast crisis. Chronic phase patients must have failed or been intolerant to Gleevec or other tyrosine kinase inhibitors.

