 - a. Patients will receive cyclosporine A (CSA) therapy beginning on Day -3 maintaining a trough level between 200 and 400 ng/mL by HPLC analysis (250 and 500 ng/ml by immunoassay). For adults the initial dose will be 2.5 mg/kg IV over 1 hour every 12 hours. For children < 40 kg the initial dose will be 2.5 mg/kg IV over 1 hour every 8 hours.
 - b. Dose adjustments will be made on the basis of toxicity and low CSA levels with a trough level of <200 mg/L (HPLC). Once the patient can tolerate oral medications, CSA will be converted to an oral form. CSA dosing will be monitored and altered as clinically appropriate.
 - c. Patients will receive CSA until Day +100. If there is no evidence of GVHD, the dose will then be tapered 10% per week starting on Day +101 and discontinued no sooner than 6 months post transplant.
2. Mycophenolate mofetil (MMF)
 - a. All patients will receive MMF at the dose of 15 mg/kg IV (based on adjusted weight) every 8 hours with a maximum of 1 gram/dose starting 4-6 hours after infusion of UCBT on Day 0. If actual body weight is < ideal weight, calculation based on actual weight is allowed. Rounding of the dose to the nearest 250 mg capsule size is also allowed. Once the patient can tolerate oral medications, MMF may be converted to an oral form.
 - b. MMF will be given every 8 hrs daily until day 40 post transplant and then in the absence of GVHD, tapered by 12%/week with MMF discontinued

after day + 96. If GVHD has been diagnosed, continued treatment and eligibility for acute GVHD protocols is at the attending physician's discretion. It is recommended in this setting that MMF be tapered after initiation of therapy for acute GVHD has been started and there is documented response. This is at the attending physician's discretion.

- c. MMF dosing to be monitored and altered as clinically appropriate.
- d. Markedly low (<40%) donor T cell chimerism after UCBT may indicate impending graft rejection. MMF should be continued at full dose or, if MMF taper has been initiated, reinstitution of full dose MMF should occur. If MMF has been discontinued, MMF should be reinitiated at full dose.

C. Umbilical Cord Blood Transplant (UCBT)

- 1. Procedures for requesting, receiving and characterizing the cord blood unit for infusion will be according to institutional protocol. Procedures for transplantation at outside centers will be reviewed and approved by the PI.

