Grade 3 or 4 adverse events (or highly unusual grade 2 adverse events) and all SAEs, which occur from the start of study treatment (pre-transplant conditioning) through Day +100 post transplant will be assessed by the investigator or qualified designee and recorded on the Case Report Form (CRF). Clinically significant AEs beyond Day 100 may also be captured at the discretion of the investigator. When a subject experiences relapse or graft failure and goes on to further treatment off protocol, adverse events will no longer be collected with the exception of death. The investigator should attempt to establish a diagnosis of the event on the basis of signs, symptoms and/or other clinical information. In such cases, the diagnosis should be documented as the adverse event and/or serious adverse event and not described as the individual signs or symptoms. The following information should be recorded:

- Description of the adverse event using concise medical terminology
- Description as to whether or not the adverse event is serious
- The start date (date of adverse event onset)
- The maximum severity (grade) of the adverse event
- A description of the potential relatedness of the adverse event to study drug or a study procedure

3) Grading of the severity of an Adverse Event

All AEs will be graded in severity according to the modified (for HSCT) NCI Common Toxicity Criteria for Adverse Events (CTCAE) Version 3.0 Appendix IX (https://ctep.cancer.gov/protocoldevelopment/electronic_applications/docs/ctcaev3.pdf). If a CTCAE criterion does not exist, the investigator should use the grade or adjectives: Grade 1 (mild), Grade 2 (moderate), Grade 3 (severe), Grade 4 (life-threatening), or Grade 5 (fatal) to describe the maximum intensity of the adverse event.

4) Attribution of Adverse Event

Association or relatedness to the study agent will be assessed by the investigator as follows:

- Definite: The event follows a reasonable temporal sequence from exposure to the investigational agent, has been previously described in association with the investigational agent, and cannot reasonably be attributed to other factors such as the patient's clinical state, other therapeutic interventions or concomitant medications; AND the event disappears or improves with withdrawal of the investigational agent and/or reappears on re-exposure (e.g., in the event of an infusion reaction).

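### The primary graft-failure endpoint does not count a donor graft that recovers, is lost and is replaced by host-cell or post-salvage recovery by day 55

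*Combined protocol and SAP*

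**What the plan says.** Section 3.A, primary endpoint 1, combines primary graft failure or rejection with secondary graft failure. Primary failure needs any one of four criteria:

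- **i.** "Absence of 3 consecutive days with neutrophils" at or above 500/µl, together with at least 50% host CD3 chimerism in blood, at day 42.
- **ii.** The same neutrophil condition "under any circumstances at day 55".
- **iii.** Death after day 28 with neutrophils below 100/µl and no sign of engraftment (donor CD3 below 5%).
- **iv.** A first count recovery that is autologous, with donor CD3 below 5% "at count recovery and without relapse".

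Secondary failure is a fall in neutrophils below 500/µl "with loss of donor chimerism after day 55".

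Section 14 sets the goal of showing a graft-failure probability significantly below a fixed 10%. It adds nothing to the definition. It gives no alpha, sidedness, cut-off or power for that comparison, and does not say whether the arms are pooled.

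**The concern.** The four primary criteria describe grafts that never took. The secondary definition describes grafts that took and were lost, but its clock starts only after day 55. A graft that took and was lost earlier can fall between the two.

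The period is not a corner of the calendar. Section 2 gives neutrophil engraftment at a median of 25 days (range 14 to 44) on protocol 2010 and 11 days (range 6 to 49) on protocol 2012. Both ranges end before day 55, so most patients can be expected to spend days or weeks with an established graft and no definition that covers its loss. That is exposure time and says nothing about how often a loss happens.

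The direction matters more than the frequency. An uncounted loss can only lower the observed failure rate, and a lower rate is what the trial sets out to show. The wording also leaves room for two assessors to class the same patient differently.

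**Working it through.** **Step 1: apply the criteria to cases.** In each case the first recovery is on days 20–22 with donor cells (donor CD3 at least 5%) and there is no relapse. *Never-achieved* means that no 3-day run at or above 500/µl has occurred by the named day. *Status* means the patient's condition on that day.

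| Case | Never-achieved reading | Status reading |
|---|---|---|
| A. Graft lost on day 40, still neutropenic at day 55, alive | i and ii fail (a run occurred), iii fails (alive), iv fails (first recovery was donor), secondary fails (too early): **not counted** | ii met: **counted** |
| B. Graft lost on days 43–50, host-cell or post-salvage run at or above 500/µl by day 55, alive | **not counted**, as for A | i fails (graft working at day 42), ii fails (counts back), iii, iv and secondary fail: **not counted** |
| C. Graft lost on day 35, neutropenic with host CD3 at least 50% at day 42, counts back by day 55 | **not counted** | i met: **counted** |
| D. Graft lost, then death on day 45 | iii applies only if neutrophils are below 100/µl and donor CD3 below 5%; earlier engraftment may exclude it | same |

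Case B is uncounted on both readings. Cases A and C depend on the reading.

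**Step 2: try the other reading of the secondary definition.** If the day-55 limit attaches only to the chimerism loss, an early neutrophil fall with chimerism loss first shown later is counted. A loss already shown by day 55 is not. Case B with chimerism loss documented by day 55 stays out.

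**Step 3: check whether chimerism sampling would date the loss.** Sections 9.B, 9.C and 9.G schedule blood chimerism at day 28 ± 3 (days 25–31) and day 56 ± 7 (days 49–63). Day 14 is added for double-unit patients at the lead centre, and Section 9.C labels the day-56 sample for lead-centre patients. No blood sample is scheduled between days 31 and 49. A loss on day 45 first seen on day 53 or day 58 could be dated to either side of day 55 by the sampling date alone.

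**Step 4: check the neutrophil condition.** Secondary failure requires a fall below 500/µl. A donor graft replaced by host cells without such a fall is not secondary failure before or after day 55. It is not criterion iv either, because the first recovery was donor.

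**Step 5: illustrate the effect on the test.** The plan has no figure to reproduce. Assumptions: exact one-sided binomial test against 0.10. Total n = 130 (Section 14).

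P(X ≤ k) = Σ from j = 0 to k of C(n, j) × 0.10^j × 0.90^(n−j)

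- Pooled, n = 130: P(X ≤ 6) = 0.0207, P(X ≤ 7) = 0.0456, P(X ≤ 8) = 0.0881. The cut-off is 7 at alpha 0.05 and 6 at alpha 0.025.
- By arm, with the enrolled split carried forward: 34/74 × 130 = 59.7 and 40/74 × 130 = 70.3. For n = 60: 0.0138 at 1 and 0.0530 at 2. For n = 70: 0.0242 at 2 and 0.0712 at 3. At alpha 0.05 the cut-offs are 1 and 2.

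In the pooled alpha 0.05 case, one uncounted loss changes the result when the true count is exactly 8. That probability is 0.0425 at a true rate of 10% and 0.1215 at a true rate of 5%, the rate that Section 2 accepts.

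**The case against.** **The definitions may adjoin by design.** Criterion i pairs neutrophils with chimerism, which is measured at a point in time, so a status reading is fair. Criterion ii then acts as a landmark at day 55 and secondary failure begins where it ends. On that reading case A is caught. This stands as far as it goes: the confirmed gap is case B and its variants, and the wider gap depends on a reading the text does not settle.

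**A reader might infer that the protocol itself expects graft loss in this period.** Section 8.B.2.d says that markedly low "donor T cell chimerism after UCBT may indicate impending graft rejection" and that "MMF should be continued at full dose or, if MMF taper has been initiated" it is to be reinstated at full dose; Section 8.B.2.b says "MMF will be given every 8 hrs daily until day 40 post transplant". But 8.B.2.d names no day, MMF can run longer when GVHD is diagnosed, and low donor chimerism also fits a patient who never engrafted. Section 12.B.2 begins "When a subject experiences relapse or graft failure and goes on to further treatment off protocol" but gives no time for the graft failure. Neither passage shows that early loss after donor recovery is expected.

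**A reader might infer a substantial false-positive rate.** With a true rate of 10% and the cut-off of 7 in 130, leaving 10%, 20% or 30% of failures uncounted would raise the chance of declaring success from 0.046 to 0.093, 0.175 or 0.304. Those shares are invented; the documents support none of them. The 0.12 in the working is no better as a measure of harm: at a true 5% the claim of less than 10% is correct, so a missed loss causes no false conclusion. Only the 0.04 concerns a wrong claim, and it must still be combined with the unknown chance that one of the eight failures falls in the gap.

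**Conclusion.** The definition is wrong as written, within limits. Donor recovery, graft loss and host-cell or post-salvage recovery, all by day 55, is not counted on any reading of the text unless criterion i was met at day 42. Early loss with persisting neutropenia is missed as well if i and ii are read as never achieved.

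The bias runs towards the trial's hypothesis. Its size cannot be estimated from the documents and may be zero. The cut-off of 7 in 130 shows only that a single patient can decide a borderline result; it rests on an assumed test, alpha and pooling, and does not say how often a loss is missed. The documents also do not give the definition behind the 10% benchmark, so it is unknown whether the benchmark counted such losses. The documents do not support saying that the endpoint materially understates graft failure; they do support closing the gap before analysis.

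**What to change.** 1. In the secondary definition, replace the day-55 limit with *at any time after initial donor neutrophil recovery*.
2. State that loss of donor chimerism with host-cell recovery counts even if neutrophils do not fall below 500/µl.
3. State whether criteria i and ii mean never achieved by the named day or status on that day.
4. Count each patient once.
5. Do not add a no-relapse condition to the main count of secondary failures. It could remove events that the current wording counts, which would again lower the rate. Show losses accompanied by relapse separately.
6. Apply this to all patients, including the 74 already enrolled (34 + 40, Section 14), from existing counts and chimerism results. Report the count under the current wording beside the new one.

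The costs are a few sentences, a re-check of 74 records and one more row in the results. There are four drawbacks:

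- A primary endpoint definition changes mid-trial while the principal investigator reviews each patient's outcome (Section 12.A), which is why both counts must be shown.
- The reported rate may be slightly higher.
- With little scheduled blood chimerism between days 28 and 56, some losses may not be confirmed or dated; these should be listed as such.
- Comparability with the 10% benchmark stays unknown and should be noted.

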2. Age, Organ Function and Performance Status Criteria

- a. Subjects must be \leq 65 years old. Patients \leq 50 must have performance status score: Karnofsky (for adults) \geq 70 or ECOG 0-1; Lansky (for children) score \geq 50 (Appendix II). Patients $>$ 50 must have Karnofsky performance score \geq 70 or ECOG 0-1 and comorbidity index $<$ 5 (Appendix II).
- b. Adequate cardiac function defined as absence of decompensated congestive heart failure or uncontrolled arrhythmia AND
 - i. left ventricular ejection fraction \geq 35% OR
 - ii. fractional shortening $>$ 22%
- c. Adequate pulmonary function defined as absence of O2 requirements **and** one of the following:
 - i. DLCO corrected \geq 70% mm Hg
 - ii. DLCO corrected between 60% - 69% mm Hg and pO2 \geq 70 mm Hg
 - iii. DLCO corrected between 50% - 59% mm Hg and pO2 \geq 80 mm Hg

Pediatric patients unable to perform pulmonary function tests must have O2 saturation \geq 92% on room air. May not be on supplemental oxygen.
- d. Adequate hepatic function. Patients with clinical or laboratory evidence of liver disease will be evaluated for the cause of liver disease, its clinical severity in terms of liver function, histology, and the degree of portal hypertension. Patients with fulminant liver failure, cirrhosis with evidence of portal hypertension or bridging fibrosis, alcoholic hepatitis, esophageal varices, a history of bleeding esophageal varices, hepatic encephalopathy, or correctable hepatic synthetic dysfunction evidenced by prolongation of the prothrombin time, ascites related to portal hypertension, bacterial or fungal abscess, biliary obstruction, chronic viral hepatitis with total serum bilirubin $>$ 3mg/dL, and symptomatic biliary disease will be excluded.
- e. Adequate renal function defined as creatinine \leq 2.0 mg/dl (adults) or estimated creatinine clearance $>$ 40 ml/min (pediatrics). All adults with a creatinine $>$ 1.2 or a history of renal dysfunction must have estimated creatinine clearance $>$ 40 ml/min.
- f. If recent mold infection, e.g., *Aspergillus*, must be cleared by infectious disease to proceed.
- g. Prior hematopoietic cell transplant: Must be \geq 3 months after previous transplant.

B. Exclusions

- 1. Pregnancy or breastfeeding.
- 2. Evidence of HIV infection or known HIV positive serology.
- 3. Uncontrolled viral or bacterial infection at the time of study enrollment.
- 4. Active or recent (prior 6 month) invasive fungal infection without ID consult and approval.

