1. For patients not on steroid therapy when the syndrome occurs: methylprednisolone should be given at 1 mg/kg IV q day for three days. If symptoms have abated, steroids should be stopped. If symptoms persist, 1 mg/kg

can be continued through six days then stopped if symptoms have abated. If symptoms persist for more than six days, the patient should be considered to have acute/hyperacute GVHD and should be treated with prolonged steroids as deemed appropriate.

2. For patients already on steroids for other reasons when the syndrome occurs: methylprednisolone should be given at a dose of 3-5 mg/kg IV (max dose 500 mg) q 12 hours x 48 hours, followed by a rapid taper to 1 mg/kg IV q 12 hours. Patients should be weaned after response as tolerated.

9. Evaluation (in addition to procedures and evaluations listed below, additional clinical evaluations as directed by the clinical team may be captured for research purposes)

Refer to FHCRC/SCCA Standard Practice Manual for Pre-Transplant Evaluation Guidelines for Allogeneic Transplant (results of tests and/or procedures conducted as per standard of care for pre-transplant workups may be used for eligibility determination if conducted within an appropriate window prior to screening) See Appendix XII for schedule of study evaluations.

A. Patient Pre-Study Screening and Evaluation Procedures

1. Medical history, allergies, previous chemotherapy, prior radiotherapy, hormonal or immunotherapy and response to treatment, end-organ toxicity and infections.
2. Karnofsky/ECOG/Lansky performance status (Appendix II).
3. Physical examination.
4. Complete blood and platelet count with leukocyte differential.
5. Basic metabolic and hepatic function panels.
6. Urinalysis.
7. Pregnancy test (blood or urine) in females of childbearing potential.
8. Viral titers (HSV, CMV, HIV, HBsAg, HBcAb, HCV, HTLV1/2).
9. PCR for CMV DNA must be done within 2 weeks prior to the start of conditioning.
10. Bone marrow aspirate (+/- biopsy as clinically indicated) collected less than one month prior to start of conditioning.
11. Electrocardiogram
12. MUGA or echocardiography with measurement of the left ventricular ejection fraction (LVEF).
13. Chest radiograph; CXR not required if chest CT performed
14. Pulmonary function tests.
15. DNA specimen from patient and from UCB unit(s) submitted to Clinical Immunogenetics Laboratory (CIL) (FHCRC patients) for chimerism studies.

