APPENDIX III: The Hematopoietic Cell Transplant-Comorbidity Index (HCT-CI)

Instructions: Circle applicable scores and provide actual value or cause of co-morbidity.

| Comorbidities | Definitions | HCT-CI weighted scores | Actual Lab Values/Comments |
|---|--|------------------------|----------------------------|
| Arrhythmia | Atrial fibrillation or flutter, sick sinus syndrome, and ventricular arrhythmias | 1 | |
| Cardiac | Coronary artery disease‡, congestive heart failure, myocardial infarction, or EF<50% | 1 | |
| Inflammatory bowel disease | Crohn's disease or ulcerative colitis | 1 | |
| Diabetes* | Requiring treatment with insulin or oral hypoglycemics, but not diet alone | 1 | |
| Cerebro-vascular disease | Transient ischemic attack or cerebro-vascular Accident | 1 | |
| Psychiatric Disturbance | Depression anxiety requiring psychiatric consult or treatment | 1 | |
| Hepatic -mild* | Chronic hepatitis, Bilirubin >ULN- 1.5 X ULN, or AST/ALT >ULN-2.5XULN | 1 | |
| Obesity* | Patients with a body mass index > 35kg/ m ² | 1 | |
| Infection* | Requiring continuation of anti-microbial Treatment after day 0 | 1 | |
| Rheumatologic | SLE, RA, polymyositis, mixed CTD Polymyalgia rheumatica | 2 | |
| Peptic ulcer* | Requiring treatment | 2 | |
| Moderate/severe renal* | serum creatinine>2mg/dl, on dialysis, or prior renal transplantation | 2 | |
| Moderate pulmonary* | DLCO and/or FEV, >65%-80% or Dispend on slight activity | 2 | |
| Prior solid tumor | Treated at any time point in the patient's past history, excluding non-melanoma skin cancer | 3 | |
| Heart valve disease* | Except mitral valve prolapse | 3 | |
| Severe pulmonary* | DLCO and/or FEV ₁ <65% or Dyspnea at rest requiring oxygen | 3 | |
| Moderate/severe Hepatic | Liver cirrhosis, Bilirubin>1.5XULN or AST/ALT>2.5XULN | 3 | |
| Please provide Karnofsky performance Score= _____ % (KPS): | | Total Score = _____ | |

Completed by (print): _____ Date _____
completed: _____

Signature: _____

*Comorbidity is currently active or patient requires medical treatment +

‡One or more vessel-coronary artery stenosis, requiring medical treatment, stent, or bypass graft

2275.00

EF indicates ejection fraction; ULN, upper limit of normal; SLE, systemic lupus erythematosus; RA, rheumatoid arthritis; CTD, connective tissue disease;
DLCO, diffusion capacity of carbon monoxide; FEV₁, forced expiratory volume in one second; AST, aspartate aminotransferase; ALT, alanine aminotransferase

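### As printed, Section 4.A.2.d excludes correctable hepatic synthetic dysfunction but names no exclusion for the uncorrectable form: probably a slip, with a narrow residual gap

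*Combined protocol and SAP*

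**What the plan says.** Section 4.A.2.d sits under the inclusion criteria and is headed by a requirement for adequate hepatic function. It first calls for a work-up: "Patients with clinical or laboratory evidence of liver disease will be evaluated for the cause of liver disease", and that evaluation also covers severity in terms of liver function, histology and portal hypertension. It then lists the conditions that bar entry. The list opens with "Patients with fulminant liver failure, cirrhosis with evidence of portal hypertension or bridging fibrosis, alcoholic hepatitis, esophageal varices", continues through "hepatic encephalopathy, or correctable hepatic synthetic dysfunction evidenced by prolongation of the prothrombin time, ascites related to portal hypertension", and closes with "chronic viral hepatitis with total serum bilirubin $>$ 3mg/dL, and symptomatic biliary disease will be excluded".

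The only item about synthetic function or prothrombin time is the one qualified as correctable: "or correctable hepatic synthetic dysfunction evidenced by prolongation of the prothrombin time". The uncorrectable form is not mentioned.

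**The concern.** A liver safety criterion would be expected to bar irreversible loss of synthetic function and, if it draws a distinction at all, to be more lenient towards a reversible one. The printed wording does the opposite. A site or monitor applying it to the letter would turn away a patient whose prothrombin time can be corrected, and would find no named ground in the list for turning away one whose prothrombin time cannot.

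Barring a correctable problem is not odd in itself, since the same sentence bars abscess and biliary obstruction without qualification. The anomaly is only that the more serious form is absent. Eligibility is verified from forms and source documents sent to central study staff (Section 12.C), so the literal wording matters. Day-200 non-relapse mortality is a primary endpoint, so the liver entry criteria should say what they mean.

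**Working it through.** The plan gives no figure to reproduce. The check is a reading of every place that could exclude a patient with uncorrectable, liver-derived prothrombin prolongation.

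1. **The list in Section 4.A.2.d.** It has 12 items: fulminant failure; cirrhosis with portal hypertension or bridging fibrosis; alcoholic hepatitis; varices; past variceal bleeding; encephalopathy; correctable synthetic dysfunction; ascites from portal hypertension; abscess; biliary obstruction; chronic viral hepatitis with bilirubin above 3 mg/dL; symptomatic biliary disease. Leaving out the item in question, 12 − 1 = 11 remain, and 0 of the 11 name synthetic function or prothrombin time. The bilirubin limit is tied to chronic viral hepatitis.

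2. **Section 4.B.** Five exclusions: pregnancy or breastfeeding, HIV, uncontrolled infection, invasive fungal infection and uncleared CNS leukemia. None concerns the liver.

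3. **Screening, Section 9.A and Appendix XII.** The 22-item list includes "Basic metabolic and hepatic function panels" but names no prothrombin or other coagulation test, and neither does the Appendix XII schedule. A site may still run one under the standard practice manual cited in Section 9. No excluding limit is stated in the protocol.

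4. **Comorbidity index, Appendix III.** The moderate/severe hepatic item is defined as "Liver cirrhosis, Bilirubin>1.5XULN or AST/ALT>2.5XULN" and scores 3; the mild item scores 1. Prothrombin time has no entry, so the abnormality itself scores 0. The index limit of below 5 applies only above age 50 (Section 4.A.2.a), and 0, 1 and 3 are each below 5.

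5. **General provisions in Section 4.A.2.d.** The adequate-function requirement and the liver evaluation apply to everyone with evidence of liver disease, and a prolonged prothrombin time of hepatic origin is such evidence. They oblige the site to assess the case but set no cut-off for synthetic function.

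6. **Who is left.** Patients whose uncorrectable dysfunction comes with fulminant failure, cirrhosis with portal hypertension or bridging fibrosis, varices, encephalopathy or ascites are excluded by name. The remainder have isolated, uncorrectable prolongation and depend on judgement under step 5.

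7. **Reach of an amendment.** Section 14 reports 34 patients in Arm 1 and 40 in Arm 2: 34 + 40 = 74. With a total of 130, 130 − 74 = 56 remain, and 56/130 = 43.1%. This is the most that an amendment could govern from that date; it does not estimate how many patients have the abnormality.

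8. **Evidence on the intended word.** The item begins with 'or' in mid-list, although five further items follow it. Replacing 'or correctable' with 'uncorrectable' restores both the grammar and the clinical sense. That makes a slip likely, but it is an inference.

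**The case against.** The strongest reply is that this is a self-evident slip, perhaps even a fault in reading the PDF, and that no transplant physician would admit irreversible synthetic failure while refusing the reversible kind. The text contains other misprints (the treatment table in Section 8.A and the body text below it spell the study drug differently), and the documents alone cannot show which of these are in the source. This part stands: the source must be checked first, and if it reads 'uncorrectable' there is nothing to change.

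It is also fair to say that the protocol is not silent. The adequate-function requirement and the evaluation of severity come before the list, Section 6 requires full evaluation under standard practice, and Section 12.C provides central review of eligibility. A reader might infer from the printed item that nothing in the protocol stops a patient with irreversible liver failure. The documents do not support that, because these provisions and the neighbouring exclusions would catch most such patients.

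What the reply does not supply is an explicit criterion. The two charitable readings also conflict. If the worse form is excluded by implication, correctable cases stay out; if the word is a slip for 'uncorrectable', they come in. The protocol does not settle which applies.

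**Conclusion.** The point holds as a wording defect of minor severity. As printed, the criterion names the milder form and omits the more serious one, and no other passage states an exclusion for isolated, uncorrectable prothrombin prolongation. The affected group is small and the documents give no count of it. Power, error rates, stopping boundaries and endpoints are untouched.

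Two stronger inferences should be resisted. First, the liver events reported in Section 2 do not measure harm from this gap. The grade 4 veno-occlusive disease, 1 of 27 (3.7%), arose on treosulfan with cyclophosphamide, which is not this trial's regimen. The grade 3 bilirubin or transaminase elevations, 7 of 56 (12.5%) on treosulfan with fludarabine, are post-treatment toxicities. Neither speaks to baseline isolated prothrombin prolongation. Second, the 43% in the working is the share of accrual still open to an amendment, not the share at risk.

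The conclusion assumes that the text available here matches the source. That 'uncorrectable' was intended is probable but not documented.

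**What to change.** Confirm the source wording of Section 4.A.2.d. If it reads 'uncorrectable', make no change. If it reads as printed, issue a short amendment so that uncorrectable hepatic synthetic dysfunction is excluded by name, in one of two ways:

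- **Replace 'or correctable' with 'uncorrectable'**, if the sponsor confirms that this was meant. The small downside is that patients with correctable prolongation, barred under the printed text, become eligible part-way through the trial, after 74 patients have enrolled.
- **Delete 'or correctable'**, so that any hepatic synthetic dysfunction shown by a prolonged prothrombin time is excluded. This admits nobody new; the small downside is slightly narrower eligibility.

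The two differ on whether correctable cases may enter, so the choice is the sponsor's clinical decision. Neither requires any change to Section 14.
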